**Table 10-1 Lower Exact 90% Two-Tailed Confidence Limits for Selected Objective Response Rate Results for 25 Subjects**

Number of Responses	Response Rate	Lower Confidence Limit
1	4.0%	0.2%
2	8.0%	1.4%
3	12.0%	3.4%
4	16.0%	5.7%

The final decision to pursue the clinical development of any disease-specific cohort will be based on safety evaluations, the complete results of the study, and other factors; fewer than 3 responses could be considered a discouraging result. When 3 or more responses are observed, there is approximately a 75% probability this occurs when the true rate is 15%, but less than 13% when the true rate is 5%. When 4 responses are observed, a 5% rate is excluded by the 90% confidence interval (CI) lower bound.

An interim futility analysis is planned for each cohort, which may have an impact on the number of subjects ultimately enrolled in Part B. The futility analysis is described in [Section 10.3.6](#).

- The Other NEC/NET and Other Solid Tumor cohorts will enroll subjects until all other disease cohorts complete enrollment, and are expected to enroll approximately 30 subjects each by the time of study completion.
- Details will be provided in the SAP.

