#### **10.3.6 Futility Analysis**

A non-binding futility analysis is planned for each cohort when 12 subjects have at least 2 evaluable tumor response evaluations after starting therapy. This analysis is designed to give a timely preliminary signal of response to consider along with cohort safety data to assess the advisability of continuing to enroll the cohort. Reported probabilities are based on exact calculations. There is a 54% chance that a result of 0 responses is observed when the true response rate is 5%. When the response rate in the population is the target rate of interest (15%); the chance of 0 responses is 14%, 1 response 30%, and 1 or more responses 96%. Therefore, observing 1 or more responses at the interim analysis would be supportive of further enrollment.

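### Section 10.3.6 overstates the chance of seeing 1 or more responses among 12 subjects at a true ORR of 15%: 96% is printed, the exact value is 86%

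*Combined protocol and SAP*

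**What the plan says.** Section 10.3.6 sets up the interim look: "A non-binding futility analysis is planned for each cohort when 12 subjects have at least 2 evaluable tumor response evaluations" after starting therapy. The result is to be weighed with the cohort's safety data. The section describes its figures as exact: "Reported probabilities are based on exact calculations".

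Two true rates are considered. For the uninteresting rate: "There is a 54% chance that a result of 0 responses is observed when the true response rate is 5"%. For the target rate of 15%: "the chance of 0 responses is 14%, 1 response 30%, and 1 or more responses 96"%.

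The section then concludes: "Therefore, observing 1 or more responses at the interim analysis would be supportive of further enrollment".

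Section 10.1, in the text under Table 10-1, refers to this look as one "which may have an impact on the number of subjects ultimately enrolled in Part B".

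**The concern.** For a fixed 12 subjects, either nobody responds or at least one subject does. The two probabilities given for those events at a 15% rate add to 110%. Rounding to whole percentages cannot produce a 10-point excess, so at least one of the two is wrong.

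The 96% is the stated chance that a cohort with the target response rate meets the criterion favouring continued enrollment, and it is the figure immediately before the sentence that draws that conclusion. Because the look is non-binding, those who review it have to weigh the result by judgment, and these probabilities are what the plan gives them for doing so. Someone who takes the 96% by itself would think a cohort at the target rate almost always passes.

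**Working it through.** **Inputs, all from Section 10.3.6**

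- Interim size: n = 12 subjects per cohort.
- True response rates: 5% and 15%. Section 10.1 uses the same two rates.
- Method: exact, taken as binomial, P(X = x) = C(12, x) · p^x · (1 − p)^(12 − x).

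**Reproducing the plan's figures**

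| Event | True rate | Formula | Exact | Plan states |
|---|---|---|---|---|
| 0 responses | 5% | 0.95^12 | 0.5404 | 54% (agrees) |
| 0 responses | 15% | 0.85^12 | 0.1422 | 14% (agrees) |
| 1 response | 15% | 12 × 0.15 × 0.85^11 | 0.3012 | 30% (agrees) |
| 1 or more | 15% | 1 − 0.85^12 | 0.8578 | 96% (does not agree) |

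Three of the four figures confirm the model and the sample size, so the fault is in the fourth. The excess is 0.96 − 0.8578 = 0.1022, or 10.2 points. The plan's own numbers lead to the same correction: 100% − 14% = 86%.

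**Could 96% be the right answer to a different question?**

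- Another event at n = 12 and 15%: 2 or more responses gives 55.7%; at most 1, 2 or 3 responses gives 44.4%, 73.6% and 90.8%.
- Another sample size at 15%: 1 or more responses reaches 96% at n = 20 (0.9612). At n = 25, the cohort size in Section 10.1, it is 98.3%.
- Another rate at n = 12: 96% needs a true rate of about 23.5%.
- The 5% rate at n = 12: 1 or more responses has probability 46.0%.

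None of these fits the stated inputs.

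**Neighbouring figures.** Under Table 10-1, Section 10.1 gives the chance of 3 or more responses among 25 subjects as approximately 75% at a true rate of 15% and less than 13% at 5%. The exact values are 74.6% and 12.7%. The plan's method is sound there too, so this is an isolated wrong number.

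**What the criterion delivers.** It is met with probability 85.8% at a 15% rate and 1 − 0.5404 = 46.0% at a 5% rate, a separation of 39.8 points. The plan states no separation; a reader who combined the printed 96% with the complement of the printed 54% would get about 50 points.

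**The case against.** The best counter-argument concerns weight. The chance of a false futility signal at the target rate is printed correctly as 14% in the same sentence, so an attentive reader can recover 86%. The rule does not depend on the 96%: the look is non-binding, is read together with safety data, and Section 11.6 lets the sponsor close a cohort at its discretion. The criterion of 1 or more responses is still reasonable at 86%. On that view this is a one-digit slip with no effect on conduct or analysis.

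All of that is true, and it limits the consequence. It does not make the figure right. The wrong number is in the favourable direction, under a claim of exact calculation, at the point where the criterion is justified.

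Three smaller caveats:

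- 86 and 96 differ by one character, so the digit should be confirmed on the PDF page. The surrounding prose is clean and gives no sign of a misread.
- Section 10 defers further detail to a SAP. The available text contains no SAP passage that repeats or corrects this number, so whether the SAP carries it is unknown.
- The look counts subjects with at least two evaluable assessments, whereas the 15% is described as a population rate. The value 85.8% assumes that rate applies to those 12 subjects. The plan's other three figures make the same assumption, so this does not rescue 96%.

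**Conclusion.** The point holds. With 12 subjects and a true response rate of 15%, the probability of 1 or more responses is 85.8%, not 96%; the plan overstates it by 10.2 points and contradicts the 14% in the same sentence. The result rests on the plan's stated interim size and rate, and on independent responses with a common rate, which is the model that reproduces the section's other figures.

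This is an error in a stated operating characteristic, not a flaw in the design. It concerns the chance of a favourable signal, not the chance of a decision to continue or stop, because the look is non-binding. It should be corrected, since the look may influence how many subjects Part B enrolls.

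**What to change.** In Section 10.3.6, change the probability of 1 or more responses at a true rate of 15% from 96% to 86%, and make the same change in the SAP if the figure is repeated there. Optionally, add that the same criterion is met 46% of the time when the true rate is 5%; this is the complement of the 54% already printed and would show both sides of the criterion together.

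The cost is one number, and a stated figure becomes less favourable. The threshold, the interim size, the cohort size and Section 10.1 stay as they are.

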#### **10.3.7 Safety Analysis**

Safety endpoints will be summarized using data from the Safety Set. Safety analyses will involve examination of the incidence, severity, and type of TEAEs reported, changes in vital signs and laboratory test results from baseline (the assessment prior to first dose) to specified time points throughout the study, and concomitant medications use.

### **10.3.7.1 Treatment Emergent Adverse Events**

TEAEs reported during the study will be coded using a Medical Dictionary for Regulatory Activities (MedDRA) dictionary. Incidence of TEAEs will be summarized by disease and cohort and the following:

- System organ class and preferred term
- System organ class, preferred term and severity

These summaries will be presented for the following subsets:

- Serious adverse events
- All adverse events
- Drug-related adverse events
- Adverse events leading to treatment discontinuation

For tables reporting AEs by severity, if a subject has multiple occurrences of an AE with the same organ class and preferred term, the most severe event will be presented.

### **10.3.7.2 Clinical Laboratory Evaluation**

Laboratory parameters will be summarized by disease and cohort at each visit. Each summary will include the values of the laboratory parameters and their change from baseline. Shift tables from baseline will be presented for laboratory values in the chemistry and hematology panels. Parameters will be classified according to the laboratory reference normal ranges. A listing will be provided for out of normal range as well as clinically significant abnormal lab values.

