### 4.1 Inclusion Criteria

1. Ability to provide written informed consent.
2. Histologically confirmed, unresectable advanced solid malignancy other than SCLC.  
*Note:* Subjects with prostate cancer must also meet the additional prostate-specific criteria in [Appendix 13.7](#).
3. Measurable disease, defined as at least one tumor lesion  $\geq 10$  mm in the longest diameter, or a lymph node  $\geq 15$  mm in short-axis measurement, assessed by computerized tomography (CT) scan (by RECIST v1.1).
4. Disease refractory to standard therapy or for which standard or curative therapy does not exist or is not considered appropriate by the Investigator.
5. DLL3-expressing malignancy based on central immunohistochemical (IHC) testing of representative baseline tumor tissue (archived tissue or on-study biopsy). Positive is defined as staining in  $\geq 1\%$  of tumor cells.
6. Eastern Cooperative Oncology Group (ECOG) performance status of 0 or 1. Refer to [Appendix 13.3](#) for conversion of performance status using Karnofsky scales, if applicable.
7. Minimum life expectancy of at least 12 weeks.
8. Subjects with a history of central nervous system (CNS) metastases must have documentation of stable or improved brain imaging for at least 2 weeks after completion of definitive treatment and within 2 weeks prior to first dose of Study Drug, off or on a stable dose of corticosteroids. Definitive treatment may include surgical resection, whole brain irradiation, and/or stereotactic radiation therapy. (Applicable to tumor types of non-CNS primary origin only).
9. Recovery to Grade 1 of any clinically significant toxicity (excluding alopecia) prior to initiation of study drug administration.
10. Satisfactory laboratory parameters:
  - a. Absolute neutrophil count (ANC)  $\geq 1,500/\mu\text{L}$ .
  - b. Platelet count  $\geq 75,000/\mu\text{L}$ .
  - c. Hemoglobin  $\geq 8.0$  g/dL.
  - d. Total bilirubin  $\leq 1.5 \times$  upper limit of normal (ULN) or  $\leq 3 \times$  ULN for subjects with Gilbert's disease.

- e. Alanine aminotransferase (ALT) and aspartate aminotransferase (AST)  $\leq 2.5 \times$  ULN ( $\leq 5 \times$  ULN if evidence of hepatic involvement by malignant disease).
  - f. Creatinine  $\leq 1.5 \times$  ULN or estimated glomerular filtration rate (eGFR)  $\geq 30$  mL/min/1.73m^2.
  - g. Serum albumin  $\geq 3.0$  g/dL
11. Last dose of any prior therapy administered by the following time intervals before the first dose of study drug:

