#### 8.1.1 Definitions

##### 8.1.1.1 Adverse Events

An AE is defined as any untoward medical occurrence in a patient or clinical investigation subject administered a pharmaceutical product and which does not necessarily have a causal relationship with this treatment. An AE can therefore be any unfavorable and unintended sign (including an abnormal laboratory finding), symptom, or disease temporally associated with the use of a medicinal (investigational) product, whether or not the event is considered causally related to the use of the product.

Such an event can result from use of the drug as stipulated in the protocol or labeling, as well as from accidental or intentional overdose, drug abuse, or drug withdrawal. Any worsening of a pre-existing condition or illness is considered an AE.

Worsening in severity of a reported AE should be reported as a new AE. Laboratory abnormalities and changes in vital signs are considered to be AEs only if they result in discontinuation from the study, necessitate therapeutic medical intervention (including interruption/dose reduction of study drug, starting or discontinuing medication, etc.), meets protocol specific criteria (refer to Sections 5.5 and 8.1 regarding toxicity management) and/or if the Investigator considers them to be AEs.

An elective surgery/procedure scheduled to occur during a study will not be considered an AE if the surgery/procedure is being performed for a pre-existing condition and the surgery/procedure has been pre-planned prior to study entry. However, if the pre-existing condition deteriorates unexpectedly during the study (e.g., surgery performed earlier than planned), then the deterioration of the condition for which the elective surgery/procedure is being done will be considered an AE.

All protocol-related AEs must be collected from the signing of the study specific informed consent until study drug administration.

In addition, AEs with onset or worsening reported by a subject from the time that the first dose of study drug is administered until 70 days have elapsed following discontinuation of study drug administration will be considered as TEAEs.

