### **8.3 Appropriateness of Measurements**

The safety measures that will be used in this trial are considered standard procedures for evaluating the potential adverse effects of study medications. AEs and, when applicable, clinical laboratory data will be graded using NCI CTCAE, version 4.03.

Response will be assessed according to RECIST v1.1 ([Eisenhauer 2009](#)), which includes standard criteria for evaluating response in solid tumors. Prostate cancer is assessed by PCWG3 criteria. The intervals of evaluation in this protocol are appropriate for disease management.

Standard tests will be performed to detect the possible presence of specific antibodies to study drug. PK assessments for drug activity are also common in clinical studies.

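### The laboratory shift tables use normal-range classes only, so they cannot show CTCAE severity; a fall from Grade 1 to Grade 4 can read as no shift

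*Combined protocol and SAP*

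**What the plan says.** Section 10.3.7.2 plans three kinds of laboratory output.

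- By-visit summaries: "Each summary will include the values of the laboratory parameters and their change from baseline".
- Shift tables: "Shift tables from baseline will be presented for laboratory values in the chemistry and hematology panels". The next sentence gives the classification rule: "Parameters will be classified according to the laboratory reference normal ranges".
- A listing: "A listing will be provided for out of normal range as well as clinically significant abnormal lab values".

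No table in Section 10.3.7 is built on laboratory grades. Section 8.3 nevertheless says: "AEs and, when applicable, clinical laboratory data will be graded using NCI CTCAE, version 4.03". Laboratory abnormalities are a named safety endpoint in Section 2.4.1, and safety is the primary objective.

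Section 4.1, item 10, admits platelets from 75,000/µL, neutrophils from 1,500/µL and albumin from 3.0 g/dL. It admits ALT and AST up to 2.5 × ULN, or up to 5 × ULN "if evidence of hepatic involvement by malignant disease".

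**The concern.** A normal-range shift table has three classes: low, normal and high. A subject who starts low and becomes much lower stays in the same class, so the table records no shift. The entry limits admit such subjects for several parameters that this drug is known or suspected to affect. Thrombocytopenia has the highest Grade 3 or worse drug-related rate reported from both earlier small cell lung cancer studies in Section 1.2, at 11% in each. Table 5-1 separates Grade 3 from Grade 4 thrombocytopenia and Grade 2 from Grade 3 or higher hypoalbuminemia. The planned shift tables can make neither distinction.

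At stake is how laboratory toxicity is described in a study whose primary objective is safety. No sample size, decision rule or dose rule depends on these tables.

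**Working it through.** The plan states no figure here to reproduce. The check classifies eligible baseline values and severe post-baseline values in two ways: by normal range and by CTCAE band.

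**Inputs.** Entry limits are from Section 4.1, item 10. Appendix 13.8 gives these bands:

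- Platelets (×10⁹/L): Grade 1 from the lower limit of normal (LLN) down to 75, Grade 2 below 75 to 50, Grade 3 below 50 to 25, Grade 4 below 25.
- Neutrophils (×10⁹/L): Grade 1 from LLN down to 1.5, Grade 4 below 0.5.
- Albumin: Grade 1 from LLN down to 3 g/dL, Grade 3 below 2 g/dL.

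Table 5-1 gives ALT/AST Grade 3 as above 5 to 20 × ULN and Grade 4 as above 20 × ULN.

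**Assumption.** The documents give no LLN. I tried 100, 130, 140 and 150 × 10⁹/L for platelets and 1.6, 1.8 and 2.0 × 10⁹/L for neutrophils. For albumin I assume an LLN above 3.1 g/dL.

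**Step 1: subjects abnormal at entry.** For platelets, neutrophils and albumin, the entry limit is the floor of the Grade 1 band. Every eligible subject below normal therefore starts at Grade 1.

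| Parameter | Baseline | Post-baseline | Normal-range table | Graded table |
|---|---|---|---|---|
| Platelets | 80,000/µL | 20,000/µL | low to low | Grade 1 to Grade 4 |
| Neutrophils | 1,500/µL | 400/µL | low to low | Grade 1 to Grade 4 |
| Albumin | 3.1 g/dL | 1.9 g/dL | low to low | Grade 1 to Grade 3 |
| ALT, hepatic involvement | 4 × ULN | 21 × ULN | high to high | below Grade 3 to Grade 4 |

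The platelet and neutrophil results were the same at every LLN tried. They hold for any LLN above the baseline value. The albumin example stops at Grade 3 because Appendix 13.8 defines Grade 4 hypoalbuminemia by clinical consequences, not by a number.

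**Step 2: subjects normal at entry.** Take an LLN of 150 × 10⁹/L and a baseline of 160. Falls to 149, 70, 40 and 20 are Grades 1, 2, 3 and 4. All four are tabulated as normal to low. A shift is shown, but its severity is not.

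**Step 3: size.** For platelets or neutrophils:

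share of Grade 4 cases shown as no shift = (Grade 4 cases with baseline below LLN) ÷ (all Grade 4 cases).

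The documents give neither count, so the share can lie anywhere from 0% to 100%.

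**The case against.** The strongest reply is that severe laboratory values are mostly captured elsewhere. Section 10.3.7.1 tabulates treatment-emergent adverse events by preferred term and severity, keeping the most severe event. Section 8.1.1.1 opens restrictively: "Laboratory abnormalities and changes in vital signs are considered to be AEs only if they result in discontinuation from the study". It then goes on to admit values that need medical intervention, expressly including interruption or reduction of study drug, values that meet protocol-specific criteria, and values the investigator considers adverse events. Table 5-1 lists Grade 4 thrombocytopenia, albumin below 2 g/dL and ALT or AST above 20 × ULN as requiring dose reduction. In a subject who continues treatment, those three examples would normally become graded adverse events. The 11% thrombocytopenia rates in Section 1.2 are themselves adverse-event rates.

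That largely stands. A reader might infer from the shift-table rule that the plan cannot report a Grade 3/4 thrombocytopenia rate, or that Grade 4 values vanish. The documents do not support either reading. The listing and by-visit changes also carry these values.

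A reader might also infer that the shift tables are needed to apply the dose rules. They are not. The neutrophil and platelet re-dosing limits in Section 5.2.3 are absolute counts, and the synopsis plans a separate summary of dose-limiting toxicities.

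Finally, Section 10 defers detail to a SAP, and nothing forbids a graded table there. However, the text available contains no such table, and the rule actually written is the less informative one.

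What the reply leaves open is narrower. The adverse-event route depends on a further dose being affected, on another intervention, or on investigator judgment. A subject with a Grade 4 nadir who stops for progression may meet none of these. The listing gives no incidence, and by-visit means, medians and extremes do not count subjects by grade. The extra blood counts required by Section 5.2.4.2 after Grade 3 or 4 hematologic events need not fall on a scheduled visit.

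**Conclusion.** The point holds as a gap in laboratory reporting. As written, the chemistry and hematology shift tables cannot show severity: worsening from an abnormal baseline in the same direction reads as no shift, and all grades reached from a normal baseline share one cell. Section 8.3's commitment to grading is not carried into any specified laboratory table. The missing output is a laboratory-based Grade 3/4 incidence that does not rely on adverse-event reporting.

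The number of subjects affected cannot be derived from the documents. The conclusion needs only an LLN above the baseline value, and the Grade 1 bands imply an LLN above the entry limit for platelets, neutrophils and albumin. It matters most for platelets, given the earlier 11% rates. It is a worthwhile, inexpensive improvement to a descriptive safety display, and it has no bearing on power, error rates or dose decisions.

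**What to change.** Add to Section 10.3.7.2, or to the SAP section that implements it:

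> For parameters with a CTCAE v4.03 grade, shift tables will show baseline grade versus worst post-baseline grade (including unscheduled values), by direction where applicable, with the number and percentage of subjects reaching Grade 3 or 4.

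Keep the normal-range tables for ungraded parameters and ungraded directions. They should not be dropped outright: Appendix 13.8 grades platelets, neutrophils and albumin only in the low direction, so high-side shifts would otherwise disappear.

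The cost is wording and programming. No new visits, samples or subjects are needed, provided unscheduled results are entered in the database. Reported Grade 3/4 laboratory rates may look less favourable than under the present tables.

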### **10.3.7.3 Vital Signs**

Vital signs, including pulse, blood pressure, temperature, height, and body weight will be summarized by disease and cohort and time point. For each assessment of vital signs, change and percent change in vital signs from baseline will be summarized by disease and cohort.

